Study participants who meet study inclusion criteria and consent to participate will complete all required baseline components before being randomly assigned to eight, 1.5 hour videoconference-delivered group sessions (2 sessions per week on average) of one of three manualized treatments: (1) cognitive therapy (CT), (2) mindfulness meditation (MM), or (3) behavioral activation skills training (AS). Telephone outcome assessors will be blind to randomization group, and participants will not be told which treatment is expected to be most beneficial. Participants will be told, however, that each of the therapies to which they could be assigned is a type of “pain self-management” intervention that previous patients have found helpful, and that the purpose of the study is to determine how these interventions work.

All measures will be assessed by research staff over telephone at pre- and post-treatment and either by telephone or online at 3-month and 6-month follow-up. We will also invite participants upon completing each assessment period to participate in an optional assessment. Additionally, primary outcome measures and hypothesized mechanism variables will be assessed (via cue-elicited, twice daily EMA methodology accessible via smart phone, tablet, laptop, and/or desktop) during an approximately 2-week Baseline Monitoring Period, throughout the Treatment Period, and throughout the initial 4-weeks Post-Treatment. During the same time

period as EMA administration, participants will also complete abbreviated weekly telephone assessments that will assess study outcome and mechanism variables. Activity level will be monitored during these time epochs via daily monitoring with ActiGraph technology. Exploratory moderator variables will be assessed at the initial screening (see Table 1).

The study uses a 3-group parallel design (see Figure 1). During their study participation, all participants will continue to receive their usual medical, psychiatric, and psychotherapeutic care.

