#### **D6g. Assessments: General Assessment Overview**

Participants will complete a Pre-Treatment extended outcome assessment with research staff following enrollment into the study. Extended outcome assessments at Pre- and Post-Treatment will be administered over the telephone by research staff blind to participant treatment assignment. The Pre-Treatment assessment may be scheduled to be done on the same day as the initial intake after the participant has provided informed consent or on a later day that works better for the participant.

During the Pre-Treatment assessment, research staff will ask participants questions on pain interference, pain catastrophizing, cognitive processes, activity level, average intensity of chronic pain over the past 7 days, mood, physical function, sleep, depression, anxiety, PTSD, medication and cannabis use, pain self-efficacy, health care use, disability due to chronic pain, engagement in activities, quality of life, employment status, weight, mindfulness, pain resilience, pain beliefs, pain medication beliefs, and perceived cognitive abilities. Effective 2020, there are also questions on COVID-19's impact on mental health and well-being. Research staff will record extended outcome assessment data on an electronic case report form in REDCap.

The entire time required to answer questions during the Pre-Treatment assessment is 45-60 minutes. Participants must complete the Pre-Treatment assessment no more than 7 weeks before starting treatment and before beginning the 2-Week EMA and ActiGraph Baseline Monitoring Period described below. Participants who do not complete the Pre-Treatment assessment within this window will not be randomized and will be offered the option to defer to a later cohort. If a participant completes the Pre-Treatment assessment but defers to a future cohort before getting randomized, they will need to redo the Pre-Treatment assessment at the time of the future cohort as we require this data within 7 weeks of treatment.

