The assessment period described above will be completed prior to initiating treatment, post-treatment (after session #8), and 3 and 6 months following the end of treatment for a total of four times. These assessment periods that occur following the start of treatment will also include questions about amount of time spent practicing skills learned in treatment, treatment satisfaction and treatment modality, the importance of various treatment outcomes, and overall improvement since the participant began the treatment program. The assessments done at 3 and 6 months following the end of treatment may be completed online by the participant via REDCap instead of verbally over the telephone with research staff. Regardless of modality, the items on both the online and verbally administrated versions of the extended assessments will be the same.

The participant will also be asked additional questions at post-treatment about their experiences in the group, as well as any feedback about the treatment program. Effective 2020, there will also be a question on COVID-19's impact during treatment. These questions will be collected by an unblinded staff member and should take approximately 15-30 minutes to complete. We will audio record and code up to 100 of these interviews until we reach saturation of themes. The audio recordings will not be labeled with any identifying information. The only identifying information that will be contained within the recordings will be participants' voices and if the staff member states a participant's name during the interview.

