Assignment to one of the three groups will be accomplished with randomization lists generated in Excel. The staff member in charge of conducting the randomization will receive training from the study statistician on how to generate the randomization lists. There is no potential for staff bias to interfere with creating these lists or randomizing participants. ***This is because the staff member conducting randomization will never have access to any person level information (other than sex and opioid use category), nor will the staff member have any direct communication with study participants at any point.*** Further, even if the staff member was familiar with person level details, this would not impact the structure of the randomization list, given that the order in which participants from each block are randomized is determined automatically by the software (using randomly generated numbers).

To further safeguard against potential bias, individuals will be randomized in the order that they become eligible for randomization (based on the completion of the pre-randomization procedures). After a participant has been randomized, the research staff member in charge of randomization will update the randomization form in REDCap to reflect the participant's treatment allocation. Only staff members who do not have access to study data during participant enrollment will know which treatment intervention corresponds with which group. Research staff will complete an electronic randomization case report form for each randomized participant that will be included with study data. The master list of participants will also be updated with the participant's assignment.

An unblinded staff member will call the participant to convey assignment and the schedule of treatment sessions. Brief (1 page) reading material specific to the treatment group will also be made available to the participant in preparation for Session 1; the reading material is informative only and not home practice. The group schedule and reading material will be provided to the participant electronically, unless the participant requests otherwise. The unblinded staff member may also provide the participant part or all of their participant treatment handbook prior to the first session (excluding instances in which the treatment mandates that a given portion of the treatment materials not be provided before a particular treatment session).

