### **Outcome variables, covariates, and mechanism variables**

Outcome variables, covariates, and mechanism variables will be assessed through a combination of extended assessments, EMA monitoring, and abbreviated weekly phone assessments. In some cases, slightly abbreviated versions of a measure will be administered during EMA assessments in order to minimize participant burden and encourage compliance (e.g., positive and negative affect, two items are asked in EMA and ten items are asked in extended assessments). The number of items for each measure in the EMAs was selected on the basis of content validity, factor loadings established during initial measure development and validation studies, brevity, and pilot data. Building on this, the minimum number of items was then selected that achieved at least good internal consistency reliability ( $\alpha \geq .80$ ) for the mechanism variables and excellent reliability ( $\alpha \geq .90$ ) for the primary outcome variable of pain interference in our pilot data. All outcome measures will be administered by research staff members blind to group allocation.

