**Table 3. Primary, Secondary, Co-Variate, and Mechanism Variables**

Variable Type	Domain	Measure (# items EMA, extended, weekly)
Primary Outcome	Morphine Milligram Equivalents (MMEs); average daily dose in past week	Self-reported opioid medication use (questionnaire, extended, and weekly)
Primary Mechanisms and Moderators	Cognitive Content Cognitive Process Activity Level Average Pain Intensity Depression Anxiety	Pain Catastrophizing – Items from Pain Appraisal Scale (3, 5, 5), Coping Strategy Questionnaire (CSQ) (0, 2, 2) Pain-Related Cognitive Process Questionnaire (PCPQ) Non-Judgment Scale (2, 6, 6) Actigraphy, Godin Leisure-Time Exercise Questionnaire (3, 3, 0), Hours spent sitting without exercising (EMA only) Numerical Rating Scale (NRS), 0-10 (1, 1, 1) PROMIS-29 Depression (0, 4, 4) PROMIS-29 Anxiety (0, 4, 4)
Secondary Outcomes	Mood Physical Function Sleep Quality Medication Use Cannabis Use Medication Use Attitudes  Post-Traumatic Stress Disorder Pain Interference	Positive and Negative Affect Schedule (PANAS) (2, 10, 0) PROMIS-29 Physical Function (4 items ext. only) Actigraphy, PROMIS-29 Sleep Disturbance (4 items ext. only) Medication Use Questionnaire (Extended only) Investigator-developed items on cannabis use (3 items ext. only) Survey of Pain Attitudes (SOPA) Medication Beliefs Sub-Scale (6 items ext. only), Pain Medication Questionnaire (PMQ) (26 items Baseline only) PTSD Checklist – Civilian Version (PCL-C) (0, 17, 0) PROMIS Pain Interference (5, 5, 0)
Secondary Mechanisms	Pain Self-Efficacy Patient Engagement Therapeutic Alliance Group Cohesion  Skills Engagement	UW Pain-Related Self-Efficacy Scale (3, 6, 0) Clinician reported patient engagement (5 items rated by clinician) Working Alliance Inventory (WAI) (12 items EMA only) Group Climate Questionnaire (GCQ-S) Engagement Scale (5 items EMA only) Duration and number of times practicing skills (EMA), number of days and duration of time practicing skills (Extended)

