## **D6r. Data Collection and Management**

### **Overview**

Data will be collected at the University of Washington via telephone, online, or in person in an outpatient setting with the following two exceptions:

1. Ecological Momentary Assessment (EMA) data, which will be entered by the participant via a web portal (desktop, laptop, tablet, mobile device);
2. ActiGraph data, which will be collected via the ActiGraph device the participant will wear during participation in the study.

All study data collected for purposes of data analysis will be de-identified, labeled with a code number that is unique to each research participant, and maintained separate from any identifying information. The participant code numbers will consist of an arbitrary number consecutively numbered in order of screening/medical record review/approach. An electronic Master List key code will be maintained that links the participants with their code number. This key code along with identifying information will be stored in a password-protected Microsoft Access database that does not contain any study data. This database will also reside in a limited access folder on the UW network drive. Only approved study personnel will have access to the Master List key code, participant identifying information, and de-identified study data. We will analyze and report participant data in aggregate form and no PHI will be entered into these analyses or reports.

De-identified data collected by research staff or online will be entered directly into a database created in REDCap, a secure HIPAA-compliant web-based system. Web forms will be created to enhance functionality and proper data entry. The REDCap system also allows researchers to create an audit trail, as well as capture an e-signature from research staff attesting to the validity of the data entered. Both pieces will be utilized during data collection (i.e., we will create audit trails and require research staff to provide electronic signatures on all our electronic case report forms). Data will be downloaded to a limited access folder on the secure UW network drive.

Ecological Momentary Assessment (EMA) data will also be encrypted and stored on a HIPAA- and IRB-compliant web-based storage database. The EMA data will also be downloaded and stored in a limited access folder on the secure UW network drive.

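### The promised assessor blind is incompletely protected: blinded callers ask treatment-related items at post-treatment, and allocation is recorded without a stated unblinded-only limit

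*Protocol*

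**What the plan says.** Blinding is promised three times in the protocol:
- D1 Synopsis: "Telephone outcome assessors will be blind to randomization group".
- D6g: "Extended outcome assessments at Pre- and Post-Treatment will be administered over the telephone by research staff blind to participant treatment assignment".
- D6p, on outcome, covariate and mechanism variables: "All outcome measures will be administered by research staff members blind to group allocation".

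D6g then says that assessments held after treatment starts "will also include questions about amount of time spent practicing skills learned in treatment, treatment satisfaction and treatment modality". Tables 1 and 4 place practice and satisfaction at post-treatment, 3 months and 6 months, and treatment modality at post-treatment only. D6g gives an unblinded staff member only the questions on group experience, program feedback and COVID-19 during treatment.

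On the allocation record, D6k describes an "electronic randomization case report form for each randomized participant that will be included with study data". It adds: "The master list of participants will also be updated with the" participant's assignment. The Overview of D6r states the access rule: "Only approved study personnel will have access to the Master List key code, participant identifying information, and de-identified study data". D6k also says that, during enrollment, the only staff who know which intervention each group stands for are those without access to study data.

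**The concern.** The primary outcome is self-reported opioid use in MMEs, collected by interview. Pain intensity, depression and anxiety are asked in the same call. A caller who knows the arm may probe or record differently by arm, even without intending to. Two routes to that knowledge are left open. The first is the conversation: practice in the three arms consists of thought records, meditation, or activity and goal logs, so talk about practice can easily name the arm. The second is the record: the assignment is stored in places that the text does not close to blinded staff.

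What is at stake is the protection that blinding is meant to give to comparisons between arms. The SAP makes such comparisons directly, using a chi-square test of dose increase, decrease or no change by condition at post-treatment and at 3 and 6 months.

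**Working it through.** No formula applies apart from simple counts. The check sets the sections side by side.

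1. **Which items stay with the blinded caller.** D6g and Tables 1 and 4 keep skills practice, satisfaction and modality in the extended assessment. At post-treatment this is a telephone call by blinded staff.

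2. **Whether the items require naming a therapy.** They do not. Table 3 describes the practice item as "number of days and duration of time practicing skills (Extended", the last word marking the extended assessment. All three arms have home practice (D6m), so every participant can answer with numbers. Satisfaction is a single global rating (PGATS, Table 3). Treatment modality is undefined. D6g soon afterwards uses modality for online versus telephone completion, and if the item means delivery mode it reveals nothing, since every arm meets on Zoom. The items prompt disclosure without compelling it. No section asks participants to withhold their arm, fixes the item order, or records a disclosure.

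3. **Access limits on records that could unblind.**
   - Attendance records (D6m): unblinded staff only.
   - Event forms with unblinding detail (F3a): unblinded staff only.
   - Home-practice documents (D6r, exceptions to separation): unblinded staff only.
   - Qualitative interviews (same place): no blinded staff.
   - Randomization form and master list (D6k): no such limit stated. D6r opens the Master List key code and study data to approved personnel without reference to blinding.

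4. **The D6k safeguard against the D6k records.** If only staff without study data know what each group is, a form showing the treatment should not sit with the study data. A coded entry would reconcile the two, but the section speaks of the participant's allocation and assignment and mentions no code. The Blinded/Unblinded Research Staff table also lists unblinded staff who manage and collect unblinded data, which does not fit the safeguard easily.

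5. **Whether callers can reach the master list.** D6r keeps the key code and identifying information in one Access database. E3d says that staff directly involved in data collection need names, addresses and telephone numbers. The staff table has blinded people collecting outcome data. If the D6k list is the D6r list, callers may be able to open it. This is an inference; no section says that they do.

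6. **Exposure.**
   - Asked the items: everyone who completes the post-treatment call. Planned 90; at 20% loss, 90 × 0.20 = 18 and 90 − 18 = 72.
   - Later contacts by a caller who learned the arm in that call: 0 to 4 weekly calls, because the window runs to 2 months after treatment and the call may follow all four; plus 0 to 2 follow-ups, which may be online. Total 0 to 6, and only if the same person calls.
   - The record route, if open, would start at randomization and cover every later call.

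**The case against.** The strongest reply is that a risk is not a failure. The practice item is numeric, the assessments are scripted (D6r, Telephone and Online Assessments), and D6g provides a response key. The most revealing questions already go to an unblinded interviewer. The practice items may already follow the MME items. In D6s participants have their medications to hand and doses are converted by formula, which leaves a caller less room to influence the result. On the records, approved personnel need not mean everyone, D6l has an unblinded staff member keep the lists of group assignments, and the D6k safeguard may imply a coded entry.

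Most of this stands against any stronger reading. A reader might infer that the blind cannot hold, or that callers work from a list showing the arm. The documents support neither. A reader might also infer that Hypotheses 1a to 1c are biased. Those are interactions between arm and a baseline moderator, so a spurious one would need reporting distorted by both arm and baseline score. For Hypothesis 1b the moderator is ActiGraph counts, downloaded only after the device comes back at the end of post-treatment monitoring. That bias is not shown.

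The reply does not remove the gap. The protocol shields four kinds of unblinding record explicitly and omits the allocation itself. It also has blinded callers raise skills practice aloud with no instruction, stated order or log.

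**Conclusion.** The assessor blind is incompletely protected as written, though not certain to fail. Exposure to the items covers all who complete the post-treatment call. The number actually unblinded could lie anywhere from none to all of them and would remain unknown, because nothing records it. The size and direction of any bias in MME cannot be derived from the documents.

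The point about the call rests only on the stated content of the assessment. The point about the records rests on the absence of a stated access limit; that callers could see the assignment further assumes that the two master lists are one and that the entry is not coded. The matter goes beyond missing detail because the primary outcome is self-reported to an interviewer and the changes cost almost nothing.

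**What to change.** 1. **D6g, Tables 1 and 4.** In any telephone extended assessment, ask skills practice, satisfaction and modality last, after MME and all other outcome and mechanism measures. Alternatively, move practice and modality at post-treatment to the existing unblinded interview, held after the blinded call. Keep the PGATS in the blinded call, asked last, because D6p requires blinded staff for outcome measures. Define modality, and align D6g with the tables on when it is asked.
2. **D6k.** Hold allocation in a REDCap form open to unblinded staff only, as for attendance records and unblinding event forms, and keep it off the master list that holds contact details. Reword the safeguard to agree with the staff table.
3. **Call script.** Ask participants at the start not to name their treatment, and have the assessor record any disclosure.

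The cost is a reordered script, a change of user rights and one tick box. If practice items move to the interview, a few may be lost: Table 2 pays nothing for it, against $25 for the extended call, and it is not held with people who attended no session. Practice is also recorded by EMA during treatment and the four weeks after.

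The SAP is dated July 2024 and written in the past tense. If collection has closed, the report should state who could open the allocation records and in what order the items were asked, and say that the blind was not verified.

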#### **D6h. Optional Assessments**

For all extended assessment periods, upon completing the main assessment, participants will be invited to participate in an optional assessment consisting of measures that were not included in the main assessment due to concerns regarding assessment length and participant burden. The optional assessment should take approximately 20-30 minutes to complete, and consists of questions regarding further responses to pain, goals, and future expectations. Optional outcome assessment data will be recorded on an electronic case report form in REDCap.

Participants are informed all optional assessments are completely voluntary, and that they may refuse to complete the optional assessments (or stop them at any time) with no effect on their payment for their completion of that particular assessment period. Participants will be informed they will not be compensated for completing the optional assessments.

#### **D6i. Re-Assessment of Eligibility**

A participant's eligibility will be re-assessed following consent and enrollment into the study to ensure that they still meet study entrance criteria. Participants will be asked similar questions to the screening questions they were asked initially. Items that could be re-assessed may include items on opioid use, pain chronicity, pain frequency, medications, and current and planned treatments, among others. Participants who are no longer eligible for the study will be thanked for their time and deferred or withdrawn from the study, depending on reason for ineligibility.

This re-assessment of eligibility may be completed up to 7 weeks before the start of treatment. Participants will not be compensated for completing this assessment.

